3.2 Primary and Key Secondary Efficacy Assessments

Primary Efficacy Assessments: Efficacy of each intervention will be evaluated with respect to lung function and asthma symptom control. Lung function will be measured prior to and post bronchodilator administration (pre-BD and post-BD). The American Thoracic Society (ATS) criteria for assessing lung function will be applied for spirometric maneuvers. A central spirometry reading center will provide quality control over-reads of the measurements and identify any issues requiring retraining of clinical staff. The primary efficacy outcome with respect to lung function is FEV₁ percent predicted pre-BD, measured in the clinic. In the event of a clinic shut-down, home spirometry assessment of the primary endpoint will be used.

Asthma symptom control will be measured using six items from the Juniper Asthma Control Questionnaire (ACQ-6) corresponding to five self-reported symptoms and self-reported rescue BD use. The primary efficacy outcome with respect to asthma control symptoms is the average score of these six items (range 0-6).

Secondary Efficacy Assessments: The use of CompEx events as a key secondary endpoint provides an outcome with statistical properties that approximate exacerbations but with a shorter follow-up time.² CompEx is a composite outcome specific to asthma that combines clinically relevant deteriorations captured by diary events with exacerbations, thereby providing an increase in power compared to using exacerbations alone. Exacerbations will be analyzed as another secondary efficacy endpoint.

CompEx events include exacerbations and deterioration events defined based on

- 1) Daily recordings of peak expiratory flow (PEF) morning/evening (L/min)
- 2) Reliever use morning/evening (doses)
- 3) Symptoms morning/evening (score 0–3) assessed from twice-daily diary recordings

The diary event can occur as defined by threshold and slope criteria within a moving window of 5-day length. Evening and morning recordings are treated as separate variables. The baseline levels of deterioration are calculated for each individual as the mean over the 5-10 days ending just before the day of randomization for each of the diary variables. No imputation of missing diary data after the randomization is performed. Deterioration criteria is assessed for each (single) diary variable for thresholds and slopes as follows:

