The Type I error probability will be controlled under the global null hypothesis (no effect on either endpoint) at $\alpha \leq 0.10$ two-sided. Power was estimated under the assumption of a within-participant, between-period correlation of responses in consecutive placebo and test treatment periods of 0.70.

Examples of treatment effects yielding a 0.3 standardized effect size include: a difference of 4.3 percent predicted FEV₁ between intervention and placebo with a SD of 14.5 percent predicted; and a difference of 0.18 in average ACQ-6 symptom scores between the intervention and placebo with a SD of 0.6.

Our analysis method ensures strong control of the Type I error probability at $\alpha = 0.10$ two-sided for each intervention. This value was chosen to reflect the experimental nature of this phase 2 proof-of-concept study. Taking into account both our stopping rule for futility and the Hochberg method for controlling multiplicity due to multiple primary endpoints, the Type I error probability is expected to equal about 0.05. Interventions that demonstrate evidence of efficacy in PrecISE with respect to at least one of the two primary endpoints may be studied further in a more fully powered phase 3 trial to provide substantial evidence of efficacy, controlling the Type I error probability at the more usual level of 0.05. Information learned from PrecISE regarding the optimal target subgroup for the intervention should be useful in developing an enrichment strategy for such a study.

No adjustment for multiplicity with respect to the multiple interventions in the study is planned. Success is defined independently for each intervention, and interventions will not be compared to each other in the efficacy analyses.

We are planning to enroll 395 participants. Assuming a study withdrawal rate of 2% a month, we anticipate that each participant will contribute data to two active interventions on average. This will allow us to accumulate required number of active treatment periods to test efficacy in all five interventions.

6. Data Sources, Documentation, and Verification of Results

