One challenge with the above approach is that a treating clinician will need to prioritize among the three outcomes (FEV₁ asthma symptoms, and loss of asthma control), for a given patient. To address this, precision medicine analysis will also be conducted combining the three outcomes. Let \mathbf{Y} be the vector of the three outcomes, rescaled so that larger values correspond to better outcomes. Specifically, for a given outcome, if larger values indicate a better outcome, the outcome remains as is; otherwise, if larger is worse, then the negative of the outcome will be used. Let \mathbf{W} be a vector of three weights between 0 and 1 whose total adds up to 1. For each possible value of \mathbf{W} (over a fine grid), the outcome weighted analysis described in the previous paragraph is repeated, including placebo as a treatment. All treatments are simultaneously compared by dividing the feature space, \mathbf{X} , into regions wherein each of the treatments is optimal for the outcome $\mathbf{W}'\mathbf{Y}$, the inner product of \mathbf{W} and \mathbf{Y} , with null regions allowed. The expected value of the resulting treatment rule is then estimated for each of the three outcomes separately using the value estimation procedure¹³, and this is repeated over all distinct values of \mathbf{W} on the grid, where m denotes the number of distinct values. A table is then created with three columns, one for each outcome, and m rows, one for each distinct value on the grid, where each entry in the table corresponds to the estimated value function for the given outcome and grid value. For each of the three columns, value function estimates are replaced by their percentiles across the m rows within each column. Now for each row, the minimum percentile across the three columns is determined, and the value of \mathbf{W} corresponding to the row that maximizes this minimum is called \mathbf{W}_* . This is the best performing combination overall in the sense that every other value of \mathbf{W} will yield a lower percentile for the worst performing outcome. This is the "minimax" optimal choice of \mathbf{W} , and all of the analyses of the previous paragraph are repeated, including the equivalence determinations, for the weighted outcome $\mathbf{Y}_* = \mathbf{W}_*'\mathbf{Y}$. This will provide an alternative clinical decision which combines the three outcomes.

References

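### The combined-outcome analysis in SAP 7.9.4 weights three outcomes in raw units after a sign change only, so the chosen weights and treatment rule depend on measurement units and lean towards FEV1

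*SAP*

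**What the plan says.** SAP 7.9.4 plans an exploratory analysis of interventions that beat placebo and whose estimated best subgroups overlap. It is run first for each of the three outcomes separately. Because a clinician would then have to choose among outcomes, a combined version follows.

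- **Preparation of the outcomes.** The vector Y is "rescaled so that larger values correspond to better outcomes". The next sentence spells this out: "if larger values indicate a better outcome, the outcome remains as is; otherwise, if larger is worse, then the negative of the outcome" is used. No division by an SD, range or other scale is stated.
- **Weights.** W is to "be a vector of three weights between 0 and 1 whose total adds up to 1". For each W on a fine grid (step not given), the regions where each treatment is optimal are found for W'Y.
- **Choice of W.** The value of each fitted rule is estimated for each outcome. Within each outcome, "value function estimates are replaced by their percentiles across the m rows within each column". The row with the largest minimum percentile gives W*, and the analysis is repeated on the outcome weighted by W*.

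The scale figures for these outcomes are in SAP Section 5. FEV1 has a 4.3-point difference "between intervention and placebo with a SD of 14.5 percent predicted"; for ACQ-6 the example is "a difference of 0.18 in average ACQ-6 symptom scores between the intervention and placebo with a SD of 0.6". ACQ-6 is a six-item average running from 0 to 6 (SAP 3.2). CompEx is modelled as an event count (SAP 7.5) and no SD is given. SAP Section 2 defines the FEV1 endpoint as percent predicted.

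**The concern.** A weight between 0 and 1 means the same thing for each outcome only if the outcomes share a scale. Here one outcome varies over tens of points and another over fractions of a point, so most weight vectors that look balanced are in effect FEV1 weightings. The rules compared in the value table are then mostly variants of the FEV1-optimal rule, and W* is selected from among them.

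The stated purpose is a clinical decision that combines three outcomes and protects the one that does worst. If the choice rests on raw units, writing FEV1 as a fraction instead of a percentage could change which drug is recommended to a patient, with no change in the data. ACQ-6 is a co-primary endpoint, so underweighting it by accident matters more than it would for a minor outcome.

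**Working it through.** **1. The plan's own figures.** Standardised effect = difference / SD. FEV1: 4.3 / 14.5 = 0.297. ACQ-6: 0.18 / 0.6 = 0.300. Both round to the 0.3 stated in SAP Section 5, so the SDs are used as given.

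**2. Two outcomes at equal weights.**
- SD ratio: 14.5 / 0.6 = 24.2.
- FEV1 share of variance, taking the two as uncorrelated: 14.5² / (14.5² + 0.6²) = 210.25 / 210.61 = 99.8%.
- Weights giving equal influence: w_FEV1 × 14.5 = w_ACQ × 0.6, so w_ACQ = 14.5 / 15.1 = 0.96 and w_FEV1 = 0.04.

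**3. The whole grid.** For each W the FEV1 share is (14.5 w1)² / [(14.5 w1)² + (0.6 w2)² + (c w3)²], where c is the CompEx SD. The documents give neither c nor the grid step, so both are assumed. Rows in which the FEV1 share exceeds one half:

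| CompEx SD (assumed) | Step 0.05 | Step 0.02 |
|---|---|---|
| 0.5 | 210/231 = 91% | 1225/1326 = 92% |
| 1.0 | 205/231 = 89% | 1198/1326 = 90% |
| 1.5 | 199/231 = 86% | 1162/1326 = 88% |
| 3.0 | 182/231 = 79% | 1066/1326 = 80% |

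The range is 79-92%. At step 0.05 ACQ-6 supplies over half the variance in 3-5% of rows for CompEx SD 0.5-1.5. With all three SDs set to 1, FEV1 does so in 70/231 = 30%.

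**4. Does the percentile step repair this?** Percentiles within a column are free of units. However, they rank rules that were each fitted to raw W'Y, and they are taken over rows crowded near the FEV1-optimal rule. A change of unit changes how the rows are spread, and hence the ranks and W*. To check, the full procedure was simulated: three drugs plus placebo, two patient features, linear effects taken as known, 300 patients, 231 rows, CompEx SD 1. The result depends on how far a drug's effects agree across outcomes, which the documents do not give.

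| Correlation of effects across outcomes | Percent vs SD-standardised: patients assigned differently | FEV1 as percent vs fraction: patients assigned differently |
|---|---|---|
| 0 | 44% | 64% |
| 0.5 | 29% | 40% |
| 0.7 | 22% | 31% |
| 0.9 | 12% | 17% |

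Repeat runs with other random scenarios moved these figures by up to 3 points. With two drugs, the minimum that triggers the analysis, and correlation 0.9, they are 10% and 14%.

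**5. What is traded away.** Mean gain over placebo in SD units for FEV1 / ACQ-6 / CompEx, three drugs:
- Correlation 0: raw 0.29 / 0.01 / 0.01; standardised 0.17 / 0.17 / 0.15.
- Correlation 0.9: raw 0.29 / 0.27 / 0.26; standardised 0.28 / 0.28 / 0.28.

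The loss on ACQ-6 and CompEx is large when effects are unrelated across outcomes and negligible when they agree closely.

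**The case against.** The strongest reply concerns consequence. SAP 7.9.4 is exploratory and is reached only if at least two interventions succeed and their subgroups overlap. Results for each outcome separately are reported first, so a combined rule that sacrificed ACQ-6 would be visible beside them; the combined rule is offered as an alternative. All of this stands, and it limits the weight of the point.

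The second reply is that equal weights have no special role. W is searched over a grid that contains ACQ-heavy rows, and rows with a low ACQ-6 or CompEx percentile are penalised. This is true and makes the procedure better than a fixed equal weighting, but step 4 shows that the selected rule still moves with the unit.

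Third, lung function, symptoms and loss of control reflect one disease, so concordant effects are plausible and the lower simulated figures may be nearer the truth. The documents cannot settle this, so the whole range is shown.

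Several stronger readings are tempting and are not supported:
- A reader might infer that FEV1 dominates nearly every weighting. The share is 79-92% and depends on an assumed CompEx SD.
- A reader might infer that the rule would also change if FEV1 were in litres, as a further example of unit dependence. Litres is a different variable, because percent predicted divides by a person-specific reference.
- A reader might infer that the 0.1-SD equivalence margin is separately faulty. It uses the SD of whichever outcome is analysed, so it scales with the weighted outcome and inherits only the choice of W*.
- A reader might infer that the second primary objective is compromised. SAP 7.8 combines test statistics, which are already free of units.

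**Conclusion.** The point holds as a defect of specification in one exploratory analysis. As written, SAP 7.9.4 aligns direction but not scale, and the combined treatment rule therefore depends on measurement units and leans towards FEV1. FEV1 supplies over half the variance of W'Y in about 79-92% of grid rows. This rests on the SAP's planning SDs of 14.5 and 0.6, an assumed CompEx SD of 0.5-3, grid steps of 0.05 or 0.02, and outcomes taken as uncorrelated.

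The effect on patients' assignments is uncertain: about 12% differ between raw and standardised outcomes at an effect correlation of 0.9 and about 44% at 0, for three drugs and CompEx SD 1. These are illustrations with known linear effects, not forecasts. The primary efficacy tests, the futility analysis and the SAP 7.8 subgroup analysis do not use W'Y and are unaffected. A reader should not conclude that clinicians would receive an FEV1 recommendation in disguise, because the separate per-outcome results stand next to it. It is a cheap correction worth making.

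**What to change.** In SAP 7.9.4, add that after the sign change each outcome is divided by its overall SD, the same sigma-hat that the section already uses for its equivalence margin, before W'Y is formed. Build the weight grid, the value table and W* on these standardised outcomes. State also the unit of FEV1 (percent predicted, if that is meant) and the form in which CompEx enters (count or rate).

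The cost is a sentence or two of text and one line of code; no confirmatory analysis changes. There is a small downside. SD scaling is a convention, and scaling by range or by a minimal important difference would be alternatives. For CompEx the SD partly reflects how often events occur rather than how much they matter, and SAP 1.3 reports a lower event rate than expected. The choice should therefore be stated openly and fixed before outcomes are unblinded. SAP 1.4 reserves changes to the blinded statisticians once an intervention has had its first unblinded review, so they should make it.
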